**In-person screening session.** Participants will be instructed to smoke *ad libitum* prior to this session. They will complete basic demographic, health and smoking history questionnaires used in our previous studies that will be reviewed and approved for eligibility by a licensed medical provider. Tobacco product consumption rates will be established using a timeline follow back procedure [95] and smoking history measures used in previous studies [70]. Psychiatric stability, including suicidality criteria, will be assessed using the PHQ-9 [96], a measure of depressive and suicidality symptoms, and the GAD-7 [97], a measure of anxiety symptoms. We will also assess nicotine dependence (Fagerström Test for Nicotine Dependence; FTND) [98] and expired CO. Any individual who is deemed ineligible for study participation for medical/psychiatric reasons will be referred to local medical and/or psychiatric resources. Any participant who spontaneously reports mood, hopelessness, anxiety and/or other symptoms suggesting a persistent change in mood, or who expresses suicidality, will activate the mental health procedures described in Appendix Z.

COVID-19 adaptation: Eligible participants will be scheduled for a virtual “in-person” screening session using an institutionally approved platform, such as Zoom.

**Phase 1: Baseline (week 1).** During this phase, participants will be instructed to smoke their usual brand *ad libitum*.

COVID-19 adaptation: No adaptations needed.

**Phase 2: VLNCC only (weeks 2-4).** During Phase 2, participants will be instructed to smoke only the VLNCCs provided by the study. At the beginning of this phase, they will be given 3 weeks' worth of VLNCCs (150% of their baseline usual brand amount). Regular or menthol will be provided according to their preference. While participants will be asked to use study cigarettes exclusively, they will not be penalized for smoking non-study cigarettes and will be asked to report any such use throughout the study. However, a specific, biochemically verified compensation plan related to VLNCC use will facilitate compliance and honest reporting, as described in the compensation and compliance section below. Smartphone diary assessments as described below will begin during Phase 2. A check-up call may be conducted around 3 days after the start of Phase 2 to troubleshoot any problems the participant may have in terms of starting a new study product. This will allow staff to address any issues that a

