Given the concerns around ECIGS, we have conducted an unplanned interim analysis of the adverse events for this protocol. Thus far, we have exposed 176 adult smokers to NIDA's VLNC combustible cigarette for up to 9 weeks and to commercially available closed-tank electronic cigarettes for up to 6 weeks (the same product being used in many other studies across the country). In terms of adverse events, similar proportions of participants have reported adverse events during the exclusive cigarette phases (18.0%) than during the phase where they are encouraged to use electronic cigarettes instead of smoking (15.3%). The most frequently reported adverse events during the electronic cigarette phases included depressive symptoms (n=4), sore throat (n=3), diarrhea (n=2), toothache (n=2), and vomiting (n=2). For the exclusive cigarette phases, the most common adverse events included cough (n=6), irritability (n=5), headache (n=4), back pain (n=2), diarrhea (n=2), limb edema (n=2), insect bite (n=2), nausea (n=2), panic attack (n=2), and urinary tract infection (n=2). No severe adverse event was reported during the electronic cigarette phases, but one was reported during the exclusive cigarette phases, brachycardia (n=1). None of these were determined to be of probable or definitive relation to the device. No serious respiratory symptoms have been reported. Our retention rate through the end of study has been 77%. The preliminary findings suggest that closed-tank electronic cigarettes are not associated with more adverse events than smoking combustible cigarettes.

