**Exclusion Criteria:**

- Unwilling to refrain from other e-cigarette use for the duration of the study, other than what is provided to them for study purposes.
- Current/recent use of certain medications:
  - a. Smoking cessation meds (past 90 days; e.g., Wellbutrin, Bupropion, Zyban, NRT, Chantix)
  - b. Certain medications to treat depression (last 14 days; e.g., Amitriptyline)
  - c. A case by case determination will be made by study physician for medication on the precautionary list (e.g., nitroglycerin)
  - d. self-reported daily use of opioids for 30 days or more on phone screen or at screening is exclusionary however PRN use is allowed (e.g., 3 to 7 days per week or less or if more frequent, use less than a month's duration.)
- Unstable medical condition as determined by the medical team
- Self-reported bronchial or respiratory infection in the last 14 days (this criterion waived during COVID-19 pandemic)
- Subject's spirometry FEV1 percentage reading is  $<50$  (severe to very severe obstruction) (this criterion waived during COVID-19 pandemic)
- Self-reported abnormal heart rhythms or cardiovascular disease (stroke, chest pain, heart attack) in the last 3 months
- Meets criteria for Major Depressive Syndrome or suicidality on the PHQ-9
- Self report of past or current diagnosis of bi-polar disorder or schizophrenia/ schizoaffective disorder
- Self-reported other tobacco use besides cigarettes or little cigars (e.g., hookah, cigarillos, smokeless tobacco, chewing tobacco, pipes, cigars, etc.) on 10 or more days in the last month.
- Recent (past 90 days), current, or planned (within the next 45 days) involvement in smoking cessation activities
- Positive urine pregnancy test at screening. Women who are one year post-menopausal, or who have had a tubal ligation or a partial or full hysterectomy will not be subject to a urine pregnancy test.
- Women that are breastfeeding or of childbearing potential and not protected by a medically acceptable, effective method of birth control while enrolled in the study. Medically acceptable contraceptives include: (1) approved hormonal contraceptives (such as birth control pills, patches, implants or injections), (2) barrier methods (such as condom or diaphragm) used with a spermicide, or (3) an intrauterine device (IUD). Contraceptives sold for emergency use after unprotected sex are not acceptable methods for routine use

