### ***Assessments and Questionnaires***

A study timeline and table of events and assessments are detailed in **Table 4**. Participants that have agreed to electronically receive questionnaires in advance of the visits will automatically be sent an email containing a participant specific link up to 5 days before the scheduled appointment. Participants will have up to 5 days prior to their appointment to access the link and complete the questionnaires. Participants who have not completed the assessments and questionnaires electronically prior to the visit will be asked to complete the assessments and questionnaires during the visit.

**PHQ-9**. Depressive symptoms will be assessed using the PHQ-9 during screening. The PHQ-9 is a multipurpose instrument for screening, diagnosing, monitoring, and measuring the severity of depression. This assessment is brief and useful in clinical practice, as it can be completed by the patient in minutes and be rapidly scored by the study staff. It can also be scored repeatedly, which can reflect improvement or worsening of depression in response to study procedures. Thus, this assessment can be administered at any visit if the participant reports depressive symptoms (see Appendix I).

**GAD-7**. Generalized anxiety will be assessed using the self-administered GAD-7 during the screening session. This assessment has 7 items that can be scored immediately by the study staff. This assessment can also be administered at any visit (see Appendix I).

**ASI-3**. The Anxiety Sensitivity Index will be used to identify whether a patient is experiencing a general sense of worry or has specific concerns relating to symptoms of stress (see Appendix GG).

**K-6**. The Kessler Psychological Distress Scale (K6) is a 5-point Likert scale used as a global measure of distress drawing from depressive and anxiety related symptomology (see Appendix DD).

**Mood History Questionnaire**. The Mood History Questionnaire is a 16-item self-report assessment that will provide information about the participant's mood in their entire life (see Appendix FF).

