### ***Protection Against Risks***

Our procedures closely follow those used in our previous clinical trials and include medical and psychiatric screening. Our study medical provider will identify participants who are medically unstable and unsuitable for participation in the study. While we expect little procedure related adverse events we will monitor participants for any adverse reactions (related and unrelated) throughout the study (see Appendices HH).

Adverse effects and concomitant medications will be assessed at each of the post-baseline visits. Participants' CO, and weight will also be measured at each in-person assessment. During the COVID-19 pandemic, we will temporarily waive collecting participants'

CO and will collect height and weight via participant self-report. The study medical provider will monitor participants' complaints of adverse events and order any follow-up procedures (laboratory assessments, etc.) as required. Adverse experience assessments will continue until 30 days following completion of the VLNC+ E-Cigarette phase.

Study medical monitor [name] and his team will monitor for respiratory and other adverse events, along with our collaborator from the Department of Pulmonology, [name]. [name] will oversee spirometric interpretation and quality control for the duration of the trial and will be consulted by [name] on respiratory-related AEs, as needed.

Confidentiality will be protected by identifying all subjects by ID numbers in all data used outside the institution (e.g., laboratory assessments). Analyses of such data are provided by sample number coded on each collection container and cannot be connected to individual participant names by the laboratory conducting the assays. Only the PI and his staff will have access to the master file linking laboratory and other data to participant names. All study data files are server maintained with limited access using password entry and log in restrictions to study staff. All information will be reported in aggregate form and individual participants will not be identified in any public reports or documents. We expect these procedures to be highly effective for protecting participant confidentiality.

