#### Adverse Event Monitoring & Concomitant Medication.

Participants will be assessed for side effects and concomitant medications using standard FDA guidelines recommended for these two procedures and recorded into the project database. Adverse event terminology and grades will be determined using the Common Terminology Criteria for Adverse Events (CTCAE), version 4.03, published by the U.S. Department of Health and Human Services.

A response time matrix will be used to guide the medical team on how long they have to respond (immediately to 48 hours) to the notice of an adverse event based on its rating. If someone from the medical team deems it clinically appropriate, the medical team or study staff may provide the subject with patient education materials printed from the MD Anderson database related to the AE they are experiencing. The subject will not be taken off study product unless the study physician or his/her personal physician recommends that we do so. Participants reporting chest pain or chest pressure will be administered a Chest Pain/Chest Pressure questionnaire (see Appendix F.) and will be triaged accordingly.

Adverse events will be reviewed by our medical personnel and the PI. Adverse event monitoring will continue up to 30 days after medication is completed. If an AE is spontaneously reported after the AE reporting period is over, the AE will be recorded in the patient's progress notes. Those AEs that are probably, possibly or definitely related to treatment will be followed until resolution or end of study, whichever comes first. In the case of reports of suicidal ideation, depression or anxiety which we believe may be related to treatment, if possible, we will engage in our normal psychological assessments. The Addiction Psychiatrist will determine the course of clinical management according to methods of good clinical practice. The PI or physician is responsible for determining the attribution of adverse events to study medication.

For this trial, AEs will be recorded according to the Recommended Adverse Event Recording Guidelines for Phase III protocols (see shaded areas of the **Table 5**). Based on the

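### After screening, no depression-severity or suicidality scale is scheduled, and no stated rule links the collected affect data to a repeat PHQ-9

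*Combined protocol and SAP*

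**What the plan says.** Under Assessments and Questionnaires, the protocol states: "Depressive symptoms will be assessed using the PHQ-9 during screening". It presents the scale as suitable for monitoring as well as screening, because it can be scored repeatedly, "which can reflect improvement or worsening of depression in response to study procedures". It then concludes: "Thus, this assessment can be administered at any visit if the participant reports depressive symptoms".

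Table 4 agrees with that text. The row for the PHQ-9 and GAD-7 has one mark, at baseline screening (Visit 0). The CES-D, K-6, ASI-3 and Mood History rows are also marked at baseline only. The text allows the GAD-7 at any visit but does not schedule it.

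The PHQ-9 also acts as a gate at entry. Table 3 excludes anyone who "Meets criteria for Major Depressive Syndrome or suicidality on the PHQ-9".

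After entry, the mental health procedures in Appendix Z start from what the participant says: "Any participant who spontaneously reports mood, hopelessness, anxiety and/or other symptoms suggesting a persistent change in mood, or who expresses suicidality". The adverse event section is also driven by reports: "In the case of reports of suicidal ideation, depression or anxiety which we believe may be related to treatment, if possible, we will engage" in psychological assessment. Separately, the section on protection against risks says: "Adverse effects and concomitant medications will be assessed at each of the post-baseline visits".

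The interim safety review, under Potential Problems & Alternative Strategies, covers 176 exposed smokers. It says: "The most frequently reported adverse events during the electronic cigarette phases included depressive symptoms (n=4").

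**The concern.** The protocol treats depressive syndrome and suicidality as reasons not to enter the study. It then schedules nothing that is described as checking whether an enrolled participant comes to meet those criteria during nine weeks on reduced-nicotine cigarettes and e-cigarettes. A scale triggered by a report cannot find a case that is not reported. The scores it does yield come from a self-selected group and may exist for only one of a participant's two dose phases.

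Two things are at stake. The first is safety: a depressive syndrome or suicidality that the participant does not disclose could be missed. The second is inferential: the counterbalanced high-versus-low comparison is the trial's best within-person contrast, yet it cannot be examined on any depression scale, although depressive symptoms have already appeared among the adverse events.

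**Working it through.** The plan states no figure that depends on this schedule, so the check is mainly a reading of the text against Table 4.

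**1. Scheduled depression scores on product.** Product is first dispensed at Visit 1. Phases 2, 3 and 4 last three weeks each, so exposure is 3 + 3 + 3 = 9 weeks, and Visits 2, 3 and 4 close those phases. Scheduled scores on product are:
- PHQ-9: 0 of 3 visits
- CES-D: 0 of 3 visits
- K-6: 0 of 3 visits

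**2. What is collected on product.**
- PANAS and MNWS: at screening and four later time points (Table 4; Measures).
- Daily diary, including negative and positive affect: phases 2 to 4.
- Random EMA, including affect: up to twice a day in phases 3 and 4, which are the two dose phases.
- Adverse events and a Health Changes Questionnaire: Visits 1 to 4.
- Planned analysis: Aim 2 compares negative affect and withdrawal between the two e-cigarette doses, using GLMM for questionnaires and diary and TVEM for EMA.

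**3. Do those measures cover the entry criterion?** They are described as measuring affect, withdrawal, craving, satisfaction or adverse events. None is described as measuring depressive syndrome or suicidality. No affect score is stated to prompt a PHQ-9 or a clinical contact. The only smartphone trigger described is at least two consecutive days without EMA data.

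**4. Stated purpose against schedule.** The text credits the PHQ-9 with showing change in response to study procedures. Change needs a later score, and the plan produces one only if a symptom is reported and staff choose to repeat the scale.

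**5. Scale of the interim observation.** Inputs are 4 depressive-symptom events and 176 exposed smokers.
- Assuming one event per participant and all 176 as denominator: 4/176 = 2.3%, exact (Clopper-Pearson) 95% CI 0.6% to 5.7%.
- The review gives 77% retention to the end of study. If only that share reached the e-cigarette phases, the denominator is about 0.77 × 176 ≈ 136, and 4/136 = 2.9%.
- If one person contributed more than one event, the proportion is lower.
- The four events are not split by dose, so no high-versus-low figure can be formed.

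**The case against.** The strongest reply is that mood is watched closely. A reader might infer that worsening mood would go unseen and could not be compared by dose. The documents do not support that: negative affect is sampled at sessions, daily and by EMA, without waiting for a complaint, and Aim 2 compares it by dose. A reader might also infer that the PHQ-9 is repeated only when symptoms are volunteered. The PHQ-9 text says reported, and a symptom elicited by the visit adverse event assessment or the Health Changes Questionnaire could lead to a repeat. The word spontaneously belongs to the mental health procedures, not to the PHQ-9 sentence. Both points stand, and they confine the concern to depression severity and suicidality.

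The interim counts might tempt a reader to conclude that e-cigarettes produce more depressive symptoms than cigarettes alone. They cannot show that. The lists give commonly reported events and are not shown to be complete, so no count for the cigarette phases can be inferred. Irritability (n=5) and panic attack (n=2) appear only in the cigarette-phase list, and overall event proportions were 18.0% in cigarette phases and 15.3% in e-cigarette phases. The e-cigarette phases always come later and last longer (3 + 3 = 6 weeks, against 1 + 3 = 4 if Phases 1 and 2 are both counted). Scaling the four events up for under-reporting is also unsupported, because the documents give no reporting sensitivity.

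It can also be said that the PHQ-9 paragraph is coherent as a case for triggered use and promises no scheduled monitoring. That is fair: this is a gap in design, not a contradiction in the text. Finally, Appendices I and Z and the content of the Health Changes Questionnaire are not in the available text and could hold further triggers. What the objection does not supply is any scheduled instrument, described in the documents, that measures depressive syndrome or suicidality after screening.

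**Conclusion.** The concern holds in a limited form. After Visit 0 the protocol schedules no depression-severity or suicidality measure. A repeat PHQ-9 is optional and report-driven, and no stated rule connects affect scores to it. The size is best put as zero scheduled depression-scale scores at the three post-exposure visits. As context, four depressive-symptom events were recorded in the e-cigarette phases, about 2.3% of 176 on the assumption of one event per person. That count gives a reason to measure systematically. It is not evidence of a product or dose effect.

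The conclusion rests on Table 4 as it can be read here, which matches the text, and on the unseen appendices adding no scheduled measure. Sample size, power and the primary analysis are unaffected. This is an inexpensive improvement to safety monitoring and to the dose comparison, not a flaw in the main inference.

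**What to change.** 1. In Table 4, mark the PHQ-9 at Visits 1 to 4. Visit 1 gives a score before product, Visit 2 follows the VLNCC-only phase, and Visits 3 and 4 give one score at the end of each dose phase.
2. Have it completed during the session, in person or virtual. Questionnaire links can go out up to five days ahead, so an advance response might otherwise wait until the visit. Handle positive responses under the mental health procedures the protocol already has (Appendix Z).
3. Reword the PHQ-9 paragraph under Assessments and Questionnaires to state scheduled use, keeping the option of extra administrations when symptoms are reported.
4. Add the PHQ-9 total, by e-cigarette dose, to the Aim 2 GLMM as an exploratory safety outcome.

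The cost is nine items at four visits (9 × 4 = 36 per participant) on the Qualtrics platform already in use, brief scoring by staff, and one amendment. The protocol itself says the scale takes minutes and is quickly scored. The drawback is an already long battery and data only from participants seen after the amendment, so the dose comparison would rest on part of the sample and should be reported as such.

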**Table 4. Study Time Line and Procedures.**

Study Timeframe	Table 4. Study Time Line and Procedures								
	Baseline Screening	Phase 1 Wk 1 (Randomization Visit)	Check -Up Call #1	Phase 2 Wk 2-4	Check-Up Call #2	Phase 3 Wks 5-7	Phase 4 Wks 8-10	30 Day Follow Up Call	
Visit #	0	1		2		3	4	FU Call	
Study Day	-29	1	8	11*	29	32*	50	71	101
ASSESSMENTS									
Phone Screen (Basic Eligibility)	X								
Informed Consent Signed	X								
Pregnancy Test	X	X		X		X	X		
Expired CO†	X	X		X		X	X		
Height	X								
Weight	X	X		X		X	X		
Urine- Compliance (cotinine, TNE, & MA)			X			X		X	
Formaldehyde DNA			X		X		X	X	
Spirometry lung function test†	X							X	
PHQ-9 & GAD-7	X								
Demographics & Smoking History	X								
Medical History	X								
Concomitant Meds	X	X		X		X	X		
Health Changes Questionnaire		X		X		X	X		
Adverse Events		X		X		X	X		
EMA Random Assessments**						X		X	
EMA Daily Diary**					X		X	X	
Product Accountability			X		X		X	X	
TLFB	X	X		X		X	X	X	
ASI-3	X								
CES-D	X								
Mood History	X								
K-6	X								
FTND	X								
MNWS	X	X		X		X		X	
QSU - Brief	X	X		X		X		X	
PANAS	X	X		X		X		X	
American Thoracic Society questionnaire (ATSQ)	X	X		X		X		X	
Purchase Tasks – Usual Brand		X		X		X		X	
Purchase Tasks – Study Cigarette				X		X		X	
Purchase Tasks – E-Cigarette						X		X	
Product Evaluation Scales – Usual Brand			X		X		X	X	
Product Evaluation Scales – Study Cigarette					X		X	X	
Product Evaluation Scales – E-Cigarette							X	X	
Implicit Association Tasks		X		X		X		X	
Perceived Health Risks		X		X		X		X	
Instruct to smoke UB	X								
Receive VLNCC		X		X		X			
Receive e-CLG				X		X			
Flavor Testing†		X							
Support/Troubleshoot				X		X			

\*if call falls on weekend, holiday or other day when the clinic is officially closed, call may be conducted on next business day; \*\*a troubleshooting call may be conducted if reports show at least 2 consecutive days of no EMA data from subject; †procedure waived during COVID-19

The Demographic, Health and Smoking History Questionnaires. These instruments expand on the data obtained during the pre-screening, providing more detailed information on demographics, health/medication history, alcohol, and other drug use, for use in the medical screening. Information on smoking history (e.g., year's smoked, previous quit attempts, relapse, current smoking rate, and other nicotine/tobacco use) is also obtained. These questionnaires have been used in our previous and current cessation studies to provide descriptive data for the study population (e.g., [158, 159]; See Appendix H).

The Fagerström Test for Nicotine Dependence (FTND). The FTND is a 6 item questionnaire that measures nicotine dependence by assessing various components of smoking behavior such as daily intake, difficulty in refraining from smoking, and time to first cigarette [98, 160]. In some studies, the scale has been found to correlate with cotinine level [37, 38] and to predict smoking treatment outcome [161]. It was modified from the most commonly used nicotine dependence measure, the Fagerstrom Tolerance Questionnaire [162]. Time to first cigarette (within 30 minutes) has been noted to be the item accounting for the majority of the variance in this scale and the one most highly correlated with multidimensional scales of nicotine dependence [163] (see Appendix Q).

The Positive and Negative Affect Scale (PANAS). The PANAS [102] is comprised of two 10-item mood scales: Positive Affect (PA) and Negative Affect (NA). Participants rate different feelings and emotions on a scale of 1-5. Various time instructions (e.g., today, past few days, past week, general, etc.) have been used with acceptably high alpha reliability ranging from .86 to .90 for PA and .84 to .87 for NA. Post-cessation PANAS negative affect is a robust predictor of relapse [164, 165] (see Appendix S).

Questionnaire on Smoking Urges -- Brief Version (QSU). The QSU Brief Form is a 10 item validated questionnaire measuring desire and intention to smoke; and anticipation of relief from negative affect and desire to smoke. The QSU has been found to be predictive of craving in laboratory studies [101] and lower scores on each of the subscales have been noted for smokers treated with varenicline or bupropion in the original clinical trials of varenicline [166] (see Appendix W).

Minnesota Nicotine Withdrawal Scale (MNWS). The MNWS is a 15-item measure of nicotine withdrawal symptoms (see Appendix R).

E-Cigarette Type Images. Subjects will indicate which types of e-cigarette they have used in the last 30 days before screening (see Appendix VV).

Abstinence. Abstinence data will be collected at all contacts using a timeline follow-back (TLFB) procedure [95, 167] as we have done in our previous studies [168]. In addition to cigarette smoking, we will also use the TLFB procedure to measure the use of other forms of tobacco and nicotine, such as cigars and e-cigarettes. Abstinence outcomes conform to the Society of Research on Nicotine and Tobacco (SRNT) [169] guidelines (see Appendix N).

